4.12 Multiple Comparisons/Multiplicity

There are two primary endpoints for efficacy analysis: CGI S A/A and BPDCL, a significant difference in either one is considered sufficient for study success. The overall significance level of the study is thus strictly controlled at a level of 5%. The Hochberg correction will be applied. If one endpoint is below the 2.5% level or if both endpoints are below the 5% level of significance the study is declared a success.

5 Efficacy Evaluation

5.1.1 Primary Efficacy Variable – CGI-S A/A

All available data will be included in the analysis.

This section covers the primary analyses of CGI-S A/A and BDPCL as well as the secondary endpoints of change over time for the same assessment.

The primary endpoints for the assessment of efficacy are the change from baseline to *Weeks 8-12* in CGI-S A/A and BDPCL. Results will be summarized by treatment and visit in terms of absolute values and changes from baseline. Besides summarizing the numerical values, the number and frequency of patients at each value on the scale will be displayed (from 1 to 7).

Boxplots of changes in CGI-S A/A will be presented by treatment arm versus each visit. In addition, individual and mean absolute values and changes from baseline will be plotted versus week.

A shift table will be produced for CGI-S A/A displaying the frequencies and proportions for the following

- At *Weeks 8-12* separately as well as an **combining the model estimates** of the endpoint values over 8-12 weeks:
 - Any decrease
 - Any increase
 - A decrease of at least 3 points
 - An increase by at least 3 points
- Any post-baseline value higher than the baseline
- Any post-baseline value lower than the baseline

The effect of treatment in terms of the change from Baseline to *Weeks 8-12* in CGI-S A/A and BDPCL will be analyzed using a likelihood-based mixed effects model for repeated measures (MMRM) with changes from baseline to each post-baseline visit as the dependent variable and the following factors:

Fixed Factors:

- Site (SITEGR1)
- Visit (AVISITN)
- Treatment Arm (TRT01P)
- Interaction between Visit and Treatment Arm
- Baseline value of the response variable*
- Psychotherapy at baseline (yes/no) (PSYBLYN)*
- Psychotherapy by baseline interaction*

*Interactions with time (visit) will be included for all covariates listed above.

The random effect of subject will be accounted for via the within-subject error correlation structure. The preferred covariance structure for the model will be unstructured (UN in SAS). If this analysis fails to converge, the model will be simplified first to Heterogeneous Toeplitz (TOEPH), then first order autoregressive with heterogeneous variance (ARH1), then compound symmetry with heterogeneous variance (CSH), followed by compound symmetry (CS). The first (co)variance structure yielding convergence will be used as the primary analysis. If a structured covariance matrix is used the sandwich estimator will be implemented to account for potential correlation matrix misspecification. The degrees of freedom will be calculated using the general Kenward-Roger approximation.

The SAS code for the primary analysis is as follows:

```
PROC MIXED data=adqs;
CLASS TRT01P(REF='Placebo') AVISITN(REF='3') SITEGR1(REF='01') PSYBLFL USUBJID;
MODEL CHG= SITEGR1 AVISITN TRT01P AVISITN*TRT01P STDBASE STDBASE*AVISITN PSYBLFL
STDBASE*PSYBLFL /s SOLUTION CL DDFM = KenwardRoger;
REPEATED AVISITN/ SUBJECT= USUBJID TYPE=UN;
LSMEANS TRT01P*AVISITN /at STDBASE=0 PDIFF CL;
ESTIMATE \see below\
Run;
```

Estimates statements averaging visits 6-8 are as follows:

Vafidemstat LSMEANS

```
ESTIMATE 'TRT01P{Vafidemstat} AVISITN{AVG 6-8}'
INTERCEPT 1
AVISITN 0 0 0.33333 0.33333 0.33333 0
TRT01P 1 0
AVISITN*TRT01P 0 0 0.33333 0.33333 0.33333 0 0 0 0 0 / e cl;
```

Placebo LSMEANS

```
ESTIMATE 'TRT01P{Placebo} AVISITN{AVG 6-8}'
INTERCEPT 1
AVISITN 0 0 0.33333 0.33333 0.33333 0
TRT01P 0 1
AVISITN*TRT01P 0 0 0 0 0 0 0 0.33333 0.33333 0.33333 0 / e cl;
```

LSDiff (Vafidemstat – Placebo)

```
ESTIMATE 'TRT01P{Vafidemstat} AVISITN{AVG 6-8} _TRT01P{Placebo} _AVISITN{AVG 6-8}'
TRT01P 1 -1
AVISITN*TRT01P 0 0 0.33333 0.33333 0.33333 0 0 0 -0.33333 -0.33333 -0.33333 0 / e cl;
```

Sites with less than two study participants per arm will be pooled. To pool sites: sites with less than two study participants per arm will be ranked within country by the number of participants within the placebo arm (higher numbers are ranked higher). Ranked sites will be pooled starting by pooling the highest ranks until the study participant requirement per arm is met. If more sites are present after the pooling criterion is met the remaining sites are pooled to meet the criterion. In the event that remaining sites do not meet the criterion they will be combined with the previously pooled group. In the event of a tie for ranking the sites, the site with the largest number in the active arm will be used. If the tie persists the sites will be ordered alphabetically or numerically (A and higher number result in a higher rank). Due to the small sample size the interim analysis will be ranked across all sites for pooling as opposed to within country.

Pooling at interim will not include country due to the small number of individuals.

The primary treatment contrast will be based on the LS means from the treatment by visit interaction term. A contrast statement will be written such that model estimates from assessments collected between weeks 8-12 are averaged to compare drug vs placebo.

The test will be a two-sided test of the null hypothesis of no difference between active treatment and placebo at *Weeks 8-12*.

A listing by subject of the CGI-S A/A scores including changes from baseline will be provided.

Individuals with no post-baseline information will have the first post-baseline visit imputed. Individuals reported to drop out for lack of efficacy will be given the baseline placebo mean. Individuals reported as dropping out for any other reason will be given the baseline group mean of their corresponding treatment.

Reasons not associated with lack of efficacy include but are not limited to the following:

- Participant Decision Due to COVID
- Lost to Follow-up
- Adverse Event
- Protocol Deviation
- Physician Decision
- Non-Compliance
- Blood Value During Randomization Visit Was Exclusionary
- Withdrawal by Subject

For the primary efficacy analyses all other missing data will be accounted for using the MMRM estimates.

The analysis of Total BPDCL will not include a categorical summary table.

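### If the unstructured covariance fails, SAP 5.1.1 pairs a sandwich standard error with Kenward-Roger, which does not calibrate it; an uncorrected sandwich then rejects about 5.6–6.7% per endpoint at nominal 5% (contingent branch, low priority)

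*SAP*

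**What the plan says.** SAP 5.1.1 prefers an unstructured covariance and then sets an order of retreat: "If this analysis fails to converge, the model will be simplified first to Heterogeneous Toeplitz (TOEPH"), then ARH1, CSH and CS. The result of that search is not a sensitivity analysis: "The first (co)variance structure yielding convergence will be used as the primary analysis".

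For any structured matrix, "If a structured covariance matrix is used the sandwich estimator will be implemented to account for potential correlation matrix misspecification". The sentence directly after it reads: "The degrees of freedom will be calculated using the general Kenward-Roger approximation". It is not limited to the unstructured model.

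The only code given is for the unstructured fit, "REPEATED AVISITN/ SUBJECT= USUBJID TYPE=UN", with Kenward-Roger on the model statement. There is no fallback code, no empirical-covariance option, no small-sample correction and no other degrees-of-freedom rule.

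The test is two-sided ("The test will be a two-sided test of the null hypothesis of no difference between active treatment and placebo"). SAP 4.12 states that "The overall significance level of the study is thus strictly controlled at a level of 5" per cent, using Hochberg: "If one endpoint is below the 2.5% level or if both endpoints are below the 5% level of significance the study is declared a success".

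**The concern.** Kenward-Roger inflates the model-based covariance of the fixed effects and takes its degrees of freedom from that matrix, treating the chosen structure as correct. The sandwich is brought in because the structure may be wrong, and it replaces that matrix. The two consecutive sentences therefore join methods that do not calibrate each other, and the reference distribution for the fallback test is not settled.

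What remains is an ordinary sandwich. It is biased downward when many parameters are estimated between subjects, and here site is a fixed factor with about 20 sites before pooling (SAP 3.1). At stake are the type I error of a prespecified primary analysis and, because SAP 4.8 runs the interim like the main efficacy analysis, the z that selects the sample-size zone.

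**Working it through.** **Inputs from the documents.** 188 randomised 1:1, 20% dropout, 150 completers (SAP 4.7); about 20 sites (SAP 3.1), with sites below two participants per arm pooled (SAP 5.1.1); six post-baseline visits in the model and a contrast averaging Weeks 8–12 (SAP 5.1.1); Hochberg thresholds of 2.5% and 5% (SAP 4.12); interim bins set for 92 patients (SAP 4.8).

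**Assumed, because the documents do not give them.** Site groups after pooling (5 to 20 at the final analysis, 12 at the interim) and the true within-patient covariance.

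**1. The plan's own figure.** n per arm = 2(z₀.₉₈₇₅ + z₀.₈₀)²/0.51² = 2(2.241 + 0.842)²/0.2601 = 73.1, so 74. At 75 per arm, power is 81.1% (normal) or 80.4% (noncentral t). 75/0.8 = 93.75, so 94 per arm and 188 in total. The sample size reproduces. The documents state no error rate for the fallback.

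**2. Analytic approximation.** With p subject-level fixed-effect parameters, an uncorrected sandwich variance is too small by a factor of about 1 − p/N. The rejection rate is then P(|Z| > z·√(1 − p/N)). Here p = site groups + 4 (site groups including the intercept, plus treatment, baseline, psychotherapy and baseline-by-psychotherapy). At N = 188:

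| Site groups | p | √(1 − p/N) | at 5% | at 2.5% |
|---|---|---|---|---|
| 5 | 9 | 0.976 | 5.6% | 2.9% |
| 10 | 14 | 0.962 | 5.9% | 3.1% |
| 15 | 19 | 0.948 | 6.3% | 3.4% |
| 20 | 24 | 0.934 | 6.7% | 3.6% |

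**3. Null simulation.** 10,000 trials per setting (Monte Carlo standard error about 0.24 points), 20% monotone dropout, fixed effects as in the SAP code, averaged Weeks 8–12 contrast, moment covariance estimates in place of REML. Rejection at nominal 5%:

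| Working structure, site groups | Uncorrected, normal | Uncorrected, t | Corrected (Mancl-DeRouen), t |
|---|---|---|---|
| TOEPH, 5 | 5.8% | 5.7% | 4.9% |
| TOEPH, 10 | 5.9% | 5.8% | 4.6% |
| TOEPH, 15 | 5.8% | 5.6% | 4.1% |
| TOEPH, 20 | 6.4% | 6.1% | 4.2% |
| TOEPH, 20, all covariate-by-visit terms | 6.0% | 5.8% | 3.8% |
| CS with autoregressive truth, 10 | 5.9% | 5.7% | 4.4% |
| CS with autoregressive truth, 20 | 6.7% | 6.4% | 3.8% |

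At nominal 2.5% the uncorrected test rejects 2.9–3.6%. A separate run of 4,000 trials with 18 site groups and a t reference gave 6.5%/3.7% (CS) and 6.1%/3.2% (TOEPH).

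**4. Source of the excess.** Moving from a normal reference to a t on about 135–150 degrees of freedom changes the rate by only about 0.1–0.3 points. Correcting the sandwich removes the excess.

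**5. Familywise rate.** Take a variance ratio of 0.90 and endpoint correlations from 0.7 to 0. The Hochberg rate is 4.6–5.0% with correct standard errors, 5.3–5.8% if one endpoint falls back, and 6.0–6.7% if both do.

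**6. Interim.** At 92 patients and 12 site groups, the simulated ratio of sandwich variance to true variance was 0.82–0.87. Then √0.82 = 0.906 and √0.87 = 0.933: the standard error is about 7–9% too small and z about 7–10% too large. A second simulation gave ratios of 0.80–0.85, which is slightly worse. The promising-zone bins in SAP 4.8 are about 0.09–0.14 wide. A correctly scaled z of 1.60 (265 completers) would read 1.60/0.933 = 1.72 (231) to 1.60/0.906 = 1.77 (201), a shift of one or two bins.

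**The case against.** **The branch is remote.** An unstructured matrix over six visits has 6 × 7/2 = 21 parameters, which 188 patients support well. In a separate check with an autoregressive heterogeneous truth and monotone dropout, an unstructured REML fit converged in 300 of 300 trials at 188 patients and 300 of 300 at 92. That was not SAS and covers only those assumptions, but it stands as a reason for low priority.

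**The sandwich is protective.** This also stands. With a compound-symmetry working model under an autoregressive truth, the model-based test rejected about 9%, against 6–7% for the uncorrected sandwich. Dropping the sandwich is not the remedy.

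**The SAP does not exclude a corrected sandwich.** True, but it names none, and the only small-sample device it names belongs to the covariance that the sandwich replaces.

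**Stronger readings that the documents do not support:**
- That the fallback cannot be run. Degrees of freedom from a model-based fit can be computed and set beside a sandwich standard error, R is also permitted (SAP 4.2, 4.3), and the documents show no software behaviour for this branch.
- That keeping Kenward-Roger causes the inflation. Step 4 shows otherwise.
- That the method will be chosen after unblinding. The order of structures is prespecified, and protocol 9.5 allows the SAP to be amended before unblinding.
- That rejection rates at interim size are type I errors. The interim z selects only a sample-size or futility zone.

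**Conclusion.** Wrong as written, in a contingent branch, and low priority. If the unstructured model fails to converge, the primary test rests on a pairing that does not calibrate the standard error. With an uncorrected sandwich it rejects roughly 5.6–6.7% per endpoint at nominal 5% and 2.9–3.7% at nominal 2.5%, so the strict 5% control in SAP 4.12 does not hold there. These rates depend on the number of site groups after pooling and on the working structure. No single value, such as the 6.4% for TOEPH with 20 site groups, should be quoted as the error rate.

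The finding does not touch the unstructured model with Kenward-Roger, which is the analysis most likely to be used. The interim effect is a possible shift of one or two sample-size bins, again only if the interim model fell back.

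**What to change.** Amend SAP 5.1.1 before final unblinding:

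- Keep the unstructured covariance with model-based Kenward-Roger as primary.
- State that if it fails, the first converging structured matrix is used with a small-sample bias-corrected empirical covariance (Mancl-DeRouen type) and between-within degrees of freedom.
- Limit the Kenward-Roger sentence to model-based fits.
- Add the fallback code beside the existing code.

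Retrying the unstructured fit first, with another parameterisation or supplied starting values, is optional. SAP 4.8 reports how patients were counted at the interim, which suggests that it has been run; the unblinded statistical team should record which covariance structure each endpoint used.

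The cost is about two sentences and a few lines of code. The corrected test is slightly conservative, at about 3.8–4.9% for nominal 5%, so p-values in the fallback branch become a little less favourable. Nothing changes if the unstructured model converges.

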For PORTICO, the Clinical Global Impression of Severity will be used focusing specifically on Agitation/Aggression (CGI-S A/A). For the CGI-S A/A, the clinician is asked, “Considering your total clinical experience with this particular population, how agitated/aggressive (i.e., ill) is the patient at this time?” Responses are on a 1-7 scale with higher scores indicating more severe illness. The CGI-S A/A should be

assessed considering the totality of collected data during the visit, including PRO performance, responses to the other ClinROs and information gleaned while talking with the patient during the visit.

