7.7.3. Visit 3 (Week 2, Day 15±2)

At Visit 3, the following activities and assessments will be performed:

- Adverse Events assessment
- Physical examination (including weight)
- Changes in concomitant medication since the last visit
- Vital signs
- Blood extraction under fasting conditions for laboratory safety assessment: hematology (including platelets) and biochemistry. If the study visit is scheduled in the afternoon/evening, fasting conditions will not be required.
- Urine drug screening
- Assess IMP compliance
- Dispensation of IMP and intake in fasting conditions of the first capsule from the new treatment box dispensed at this visit. If the study visit is scheduled in the afternoon/evening, fasting conditions will not be required.
- Provide snack/meal
- COAs (Note: for the STAI, Form Y-1 only)

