4.2 General Statistical Considerations

'Baseline' is defined as the last available non-missing pre-treatment assessment. The average of screening and baseline values will be used as the baseline for effectiveness analysis. In the instance where only one value is present that value will be solely used as baseline. Change from baseline is calculated as visit value – baseline visit. 'End of Study' is defined as the last available post-treatment assessment. 'Treatment Day' will be calculated relative to the date of randomization (i.e., Treatment Day = Assessment Date - Randomization Date + 1). For safety summaries, the last pre-treatment measurement is defined as the baseline value.

When duration is calculated for an event (e.g., Adverse Events) and starting and ending date and time are both available, then, duration will be calculated as 'End datetime' – 'Start datetime' and presented in outputs in X day(s) hh:mm format. If time is missing or partially missing for either the end or the start of the event, then, duration will be calculated in days instead as 'End Date' – 'Start Date' + 1 Day.

Continuous data will be summarized in terms of the mean, standard deviation (SD), median, minimum, maximum, and number of observations, unless otherwise stated. The minimum and maximum will be reported to the same number of decimal places as the raw data recorded in the database. The mean, median, lower quartile and upper quartile will be reported to one more decimal place than the raw data recorded in the database. The SD will be reported to two more decimal places than the raw data recorded in the database. In general, the maximum number of decimal places reported shall be four for any summary statistic.

Categorical data will be summarized in terms of the number of subjects providing data at the relevant time point (n), frequency counts and percentages. Any planned collapsing of categories will be detailed in the SAP text and the data displays.

Percentages will be presented to one decimal place. Percentages will be calculated using 'n' as the denominator, unless otherwise stated.

Clinical rating scales may be summarized both as a continuous and as a qualitative variable, depending on the context.

Changes from baseline in categorical data will be summarized using shift tables where appropriate.

P-values greater than or equal to 0.001, in general, will be presented to three decimal places. P-values less than 0.001 will be presented as "<0.001".

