The estimator for the primary estimand is a likelihood-based mixed model for repeated measures (MMRM). The primary analysis will include all available assessments. Individuals with no post-baseline information will have the first post-baseline visit imputed. Individuals reported to drop out for lack of efficacy will be given the baseline placebo mean. Individuals reported as dropping out for any other reason will be given the baseline group mean of their corresponding treatment.

5. *Sensitivity analyses and missing data.*

To assess the effect of averaging efficacy for visits corresponding to weeks 8-12 on the primary outcome, a sensitivity analysis will be implemented in which the primary efficacy analysis will be run for visits associated with weeks 8, 10, and 12 separately. As clinical studies are limited in the ability to schedule visits on the exact prespecified study day a continuous time model that extracts the predicted estimates on the prespecified study day will be used as a sensitivity model to assess the degree to which windowing affects the outcome. Additional sensitivity models will be run with multiple imputation within each treatment arm. The first analysis (missing at random; MAR) is meant to estimate the treatment effect if all study participants continued on their current trajectory within the treatment group by imputing the missing data within associated treatment groups. The second analysis (missing not at random; MNAR) imputation is performed for all study participants relative to the placebo group only. This analysis assumes study participants at dropout progress similarly to the placebo group. This analysis will provide a lower bound estimate of the effect. A tipping point analysis using multiple imputation will also be performed.

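### Patients with no post-baseline score get a group baseline mean at Visit 3, so sicker-than-average patients are scored as improved and milder ones as worsened

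*SAP*

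**What the plan says.** SAP 5.1.1 states: "Individuals with no post-baseline information will have the first post-baseline visit imputed". The protocol schedule makes that Visit 3, Week 2. SAP 4.6(4) and 5.1.1 then give two rules. For lack of efficacy: "Individuals reported to drop out for lack of efficacy will be given the baseline placebo mean". For everyone else: "Individuals reported as dropping out for any other reason will be given the baseline group mean of their corresponding treatment".

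The primary model is an MMRM "with changes from baseline to each post-baseline visit as the dependent variable", and SAP 4.2 defines the outcome: "Change from baseline is calculated as visit value – baseline visit". The covariates include "Baseline value of the response variable", with a visit interaction. SAP 5.1.2 applies the same analysis to the BPDCL.

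Other sections disagree about whether anything is imputed:

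- SAP 4.5 and protocol 9.2 define the Full Analysis Set (FAS) as all randomised patients, so patients with no post-baseline score are included. The protocol synopsis requires at least one post-baseline efficacy score, which would leave nobody to impute.
- SAP 4.11 (Treatment Compliance) says that the primary analysis uses all available data and does not impute missing values.
- Protocol 9.6 rules out imputation at the interim. SAP 4.8 runs the interim as the main efficacy analysis and drops only the sensitivity analyses.

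**The concern.** A raw score that is the same for everyone in a group is placed in a model of change from each patient's own baseline. The change recorded for a patient nobody saw again therefore depends only on how far that patient's baseline lies from the group mean. On the CGI-S A/A, "Responses are on a 1-7 scale with higher scores indicating more severe illness" (protocol 7.2.7), so a negative change is an improvement.

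The rule also separates lack of efficacy from other reasons, yet the two values it assigns are both baseline means of randomised arms, which are equal in expectation.

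At stake is the content of the primary estimator for both endpoints: individual responses that were never observed, and a distinction by reason for dropout that does nothing systematic. If SAP 4.8 is followed, the rule also feeds the interim sample-size decision.

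**Working it through.** **Plan's own figure.** The imputation rule carries no stated figure. The design effect gives the scale: n per arm = 2(2.2414 + 0.8416)²/0.51² = 73.1, so 74, against 75 in SAP 4.7. Noncentral-t power at 75 is 80.4%, and 75/0.8 = 93.75, so 94 per arm and 188 in total. The plan's figure is reproduced.

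**Step 1: imputed change.** Let b be the patient's baseline and m the group baseline mean. Imputed change = m − b, an exact line of slope −1 on baseline with no residual error. The documents give no baseline means, so these are illustrations:

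| Scale, assumed mean | Own baseline | Imputed change |
|---|---|---|
| CGI-S A/A, 4.8 | 4 | +0.8 |
| CGI-S A/A, 4.8 | 6 | −1.2 |
| CGI-S A/A, 4.8 | 7 | −2.2 |
| BPDCL, 130 | 90 | +40 |
| BPDCL, 130 | 170 | −40 |

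**Step 2: the lack-of-efficacy rule.** In the placebo arm both rules give the placebo baseline mean, so they are identical. In the vafidemstat arm they differ by the chance difference in baseline means. This has expectation 0 and SD √(2/94) = 0.146 baseline SD (95% range ±1.96 × 0.146 = ±0.29). Its sign is arbitrary. In simulation with 5-10% early dropout per arm (assumed), applying one rule or the other to all such patients moved the late contrast by less than 0.001 SD on average.

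**Step 3: when the rule flatters a patient.** Suppose the expected Visit 3 change is μ + β(b − m). The imputed change minus this is −(1 + β)(b − m) − μ. With assumed μ = −0.3 and β = −0.35, it equals −0.65(b − m) + 0.3, which is zero at b − m = 0.46 SD. Above that point the rule credits more improvement than the model would predict; below it, less. The direction therefore depends on who leaves.

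**Step 4: effect on the Weeks 8-12 contrast** (baseline SD units, negative favours drug, 94 per arm, likelihood fit in two steps). All rates, slopes and correlations are assumptions.

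| Early dropout, active/placebo | True effect | No imputation | SAP rule | Own baseline |
|---|---|---|---|---|
| 5%/5%, unrelated to baseline (A) | −0.51 | −0.510 | −0.505 | – |
| 10%/5%, unrelated to baseline (A) | −0.51 | −0.512 | −0.491 | – |
| 10%/5%, sicker leave (A) | −0.51 | −0.512 | −0.506 | – |
| 10%/3%, sicker active leave (B) | 0 | +0.002 | −0.020 | +0.034 |
| 10%/3%, sicker active leave (B) | −0.51 | −0.510 | −0.518 | −0.465 |
| 10%/3%, sicker active leave (C) | 0 | −0.002 | −0.027 | +0.035 |

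A: 3,000 trials; placebo change −0.4 at Visit 3 and −0.6 late; drug effect −0.15 at Visit 3; residual correlation 0.6. B: 4,000 trials; placebo change −0.3 at Visit 3 and −0.5 late; 15% later dropout. C: a separate run of the same kind as B.

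In C the SAP rule lies 0.025 from no imputation (−0.027 against −0.002) and 0.062 from own-baseline imputation (−0.027 against +0.035). In A it attenuates the effect, by 0.021 in the second row. The sampling SD of the contrast in A was about 0.13.

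**The case against.** **Bias toward vafidemstat.** A reader might infer that the rule favours the drug. The documents do not support that. The error is symmetric, they give only 20% overall dropout, and nothing says that sicker vafidemstat patients leave before Week 2. A pro-drug shift needs that pattern; under other patterns the rule slightly attenuates the effect. This objection stands.

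**A failed penalty.** One might also infer that the lack-of-efficacy rule was meant as a penalty. The SAP never calls it one. What can be said is that it has no systematic effect. Reading the baseline mean as a mean change at baseline does not rescue it: both rules would then give zero.

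**Few patients are affected.** Withdrawing patients are asked to complete an end-of-study visit, and SAP 4.2 windows early-termination assessments into the nearest scheduled visit. Only Visit 3 is filled, and Weeks 8-12 are reached only through within-patient correlation. This stands and explains the small size.

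**Sensitivity analyses are already planned.** SAP 5.1.1.1 has multiple imputation under missing at random, placebo-based imputation and a tipping point. They are useful, but they do not remove the rule from the primary estimator. The baseline covariate does not absorb it either, because the imputed points follow a slope of −1 that observed data do not share.

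**Own-baseline imputation is no cleaner.** It too is a single imputation without residual error, and in scenarios B and C it moved the contrast further from the truth than the SAP rule. With no placebo change assumed, the order reversed (own baseline +0.018, SAP rule −0.036, true effect 0). It is a conservative choice, not a correction.

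**Conclusion.** The point holds as a wrong stated rule in the primary estimator, not as missing detail. That the imputed change equals group mean minus own baseline follows from SAP 4.2 and 5.1.1 alone and needs no assumption. So does the absence of any systematic effect of the lack-of-efficacy rule under 1:1 randomisation.

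The size does rest on assumptions: early dropout of 3-10% per arm, its relation to baseline, the placebo change and the correlations. Under these the Weeks 8-12 contrast moves by about 0.01 to 0.06 SD depending on scenario and comparator, with the upper end measured against own-baseline imputation. That is small beside a design effect of 0.51 and a sampling SD near 0.13, and the sign is set by who leaves. It should not be presented as a threat to the trial's conclusion. It merits correction because the plan contradicts itself here and the change costs almost nothing.

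**What to change.** 1. Delete the group-mean imputation from SAP 4.6(4) and 5.1.1. State that the likelihood-based MMRM uses observed post-baseline data only, as SAP 4.11 already says, and move that sentence out of the compliance section.
2. Handle patients with no post-baseline score in the planned multiple-imputation analyses (missing at random, placebo-based, tipping point). The SAP 5.1.1.1 imputation model already predicts Week 2 from the patient's own baseline. Own-baseline imputation (change = 0) can be added as a conservative sensitivity analysis.
3. Reconcile the FAS in the protocol synopsis with protocol 9.2 and SAP 4.5, and SAP 4.8 with the protocol 9.6 statement on imputation at the interim. SAP 4.8 already reports events at the interim, so record whether the rule was applied there, and date the amendment before final unblinding.

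Cost: a few SAP sentences and no new data. The downside is that patients with no post-baseline score contribute no outcome to the primary MMRM and enter only through the sensitivity analyses. Report their number by arm and reason.
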